## 3.4 Study Endpoints

### 3.4.1 Primary Study Endpoint

The primary outcomes (size-appropriate CRS use and CPaSS) will be assessed in-person at Month 12. The secondary outcome, the CPaSS trajectory, is a measure of correct and consistent restraint use in response to the intervention and will be assessed by scoring photographs submitted by caregivers (Months 1-5; 7-11) and collected by the study team (Months 6 and 12). Photographs will be scored using the CPaSS tool by research team members blinded to the treatment group.

## 4 Study Population and Duration of Participation

### 4.1 Duration of Study Participation

Caregivers that agree to enroll in the study will participate for up to 12 months. This includes the screening process, baseline visit, monthly photo requests, and two follow-up visits (6 and 12-months). Study participation by the caregiver/parent will end after the 12-month follow up visit.

### 4.2 Total Number of Subjects and Sites

To test the Tiny Cargo, Big Deal Intervention, we anticipate the need to screen 10,000 caregivers to recruit 900 caregivers who will be enrolled in the study and randomized to intervention or control. All recruitment will occur in the Emergency Department (ED) at Lurie Children's Hospital of Chicago (LCH) or remotely via phone/email/text message. With this most recent IRB modification (3/26/21), we will also add recruitment via flyers in patient treatment rooms from Lurie Children's affiliate EDs (e.g., Central DuPage, Northwest Community) and Lurie Children's Immediate Care Centers (Lincoln Park and Northbrook).

### 4.3 Inclusion Criteria

Caregivers (parents or legal guardians) meeting inclusion criteria will be approached to take the screening survey in the ED waiting room or ED treatment rooms during natural breaks in treatment/care or remote recruitment will include email, text message and/or telephone calls to families of children who sought care in the Lurie Children's ED. With this most recent IR modification (3/26/21), we will also add remote recruitment via flyers from Lurie Children's

# Emergency Medicine Prospective Protocol

affiliate EDs (e.g., Central DuPage, Northwest Community) and Lurie Children's Immediate Care Centers (Lincoln Park and Northbrook).

For in-person recruitment, research assistants will use the LCH ED electronic tracking board to look for participants with the following inclusion criteria to approach them to take the screening survey and will confirm upon approach that the child and family meet the following inclusion criteria:

- Child (patient) of caregiver is age 6 months to 10 years old at screening
- Child (patient) of caregiver is seeking care in the ED for a noncritical injury or illness or received care in the past 6 months
- Caregiver/parent is the legal guardian of the child seeking care in the ED
- Child of caregiver is less than 55 inches tall

Caregiver speaks English or Spanish (NOTE: Spanish intervention components will be submitted for IRB review after initial IRB approval is granted. The research team will only recruit English-speaking caregivers until IRB approval is granted for the recruitment of Spanish-speaking caregivers) Caregiver is 18 years old or older

Caregiver/parents that complete the screening survey and meet the additional study inclusion criteria will have the opportunity to enroll in part 2 the study. The study inclusion criteria required for enrollment are:

- Caregiver owns a smart phone
- Caregiver rides/drives/travels at least once a week with their child in a car, truck, or van
- Caregiver screens positive for sub-optimal child passenger safety behaviors or who report plans for premature transition to a less protective restraint in the coming 6 months (**see section 9 for additional document, "screen eligibility sheet," that RCs will use to determine eligibility of caregiver for part 2 of the study based on their responses within the screening survey**)
- If enrolled, caregiver is willing to travel to follow-up locations (not applicable as study tasks have gone fully remote)
- If enrolled, caregiver is willing to receive and send text messages each month as part of the study
- Child of caregiver rides unrestrained in the past month
- Child of caregiver rides in the front seat in the past month

The remote recruitment process will include outreach via email, text message, phone, postcard, ED room flyer, and MyChart Research Recruitment to caregivers of children age 6 months to 10 years who were seen in the Lurie Children's ED in the 6 months prior to the current data. Eligibility for contact for screening will be determined based on Epic reports that will include child age, child weight, ZIP code of their home address, and language preference of English or Spanish. Potential participants will be screened to determine if they attest to being the parent/legal guardian and at least 18 years of age. Caregiver self-report of child's height will be used.

Remote recruitment will also include flyers in patient treatment rooms at LCH affiliate sites – families that may not have visited the LCH ED. Caregivers that are recruited remotely via a the flyers will confirm the above criteria in the screening survey.

## 4.4 Exclusion Criteria

Caregivers (participants) will not be approached to be screened for this study if they meet any of the exclusion criteria shown below. Special care will be taken to screen out caregivers of deceased children prior to recruitment efforts.

# Emergency Medicine Prospective Protocol

For remote recruitment, research coordinators will use EPIC reports to verify the following criteria and/or will allow the screening survey and conversation with the caregiver to identify for the following exclusion criteria.

For in person recruitment, research coordinators will use LCH ED electronic tracking board and conversation with caregiver to identify for the following exclusion criteria:

- Caregiver does not understand/speak English (or Spanish once IRB approval granted for recruitment of Spanish-speaking participants)
- Child of caregiver is seeking care for a critical illness or injury: (ESI=1), treatment being given in ED trauma bay or a negative pressure room, or child requires a sepsis huddle.
- Child of caregiver is seeking treatment for a new long-term diagnosis (e.g., diabetes, cancer) (not applicable while recruiting remotely)
- Child of caregiver has anticipated need for admission
- Child of caregiver is seeking care for child abuse/neglect and/or Child Protective Services is involved in treatment
- Child of caregiver is seeking care that requires intensive psychosocial services (e.g., sexual assault, psychosis/active suicidal/homicidal ideation/attempt)
- Child of caregiver is seeking treatment for a motor vehicle related injury.
- Child of caregiver is too tall for study (height = >54 inches tall)
- Child of caregiver is classified as "break the glass"
- Caregiver has already refused the study twice
- Child of caregiver is already enrolled in another study at LCH (e.g., IMPROVE) (not applicable while recruiting remotely)
- Caregiver completed this study's screen for this child within the past 6 months
- Caregiver is already enrolled in this study for this child or another one of their children
- Caregiver is unable to provide consent (not legal guardian of child seeking care in ED)
- Caregiver is under 18 years of age
- Caregiver lives out of the state or out of the country
- Caregiver is deaf, blind, or visually impaired and unable to provide informed consent

Participants (caregiver/parents) that complete the screening survey and meet the additional study exclusion criteria will also be excluded from enrolling in the study. The study exclusion criteria for enrollment are:

- Child of participant requires a wheelchair or other special needs seating when traveling in vehicles

## **4.5 Subject Recruitment**

### Competing studies in ED:

The research study called IMPROVE (IRB #00117338) will be recruiting patients in the ED at LCH and will overlap with our study population in the following patient ages (4-10 years).

If a child comes into the ED at LCH between the ages of 4-10 years of age, and meets criteria for IMPROVE, then our study team will communicate with the Research Coordinators of IMPROVE and allow them to approach the child/family first. If the child becomes enrolled in IMPROVE, then our study team will exclude the child/family from our study and will not approach them. However, if the child is determined to be ineligible for IMPROVE and/or decides not to participate in IMPROVE, then our study team will approach the family to see if they would like to enroll.

# Emergency Medicine Prospective Protocol

If this plan causes any problems with the enrollment numbers for Tiny Cargo, Big Deal, then procedures will be put in place to revise this process as necessary.

\*\* not applicable while recruiting remotely

## Recruitment procedures:

Research Assistants will utilize the LCH ED electronic tracking board to continuously monitor incoming patients that meet study inclusion criteria during recruitment shifts. A waiver of informed consent will be requested for review of the ED Electronic Medical Record (EMR)/Patient Tracking board at LCH to determine which families to approach for screening. Adult caregivers of children 6 months to 10 years old, who bring their child to the LCH ED for any non-critical illness or injury, will be approached for eligibility screening.

All participants (caregivers/parents) meeting the basic list of inclusion criteria will be approached by an RA either in the ED waiting room or the child's (patient) ED treatment room to enroll in the part 1 screening survey. Remote recruitment will include email, text message, telephone calls, mailed postcards, ED discharge paperwork, and MyChart Research Recruitment messages to families of children who sought care in the Lurie Children's ED. With this most recent IR modification (3/26/21), we will also add recruitment via flyers from Lurie Children's affiliate EDs (e.g., Central DuPage, Northwest Community) and Lurie Children's Immediate Care Centers (Lincoln Park and Northbrook).

An informational handout sheet will be used by the RA to explain the study and obtain verbal consent to participant before data collection begins. During remote recruitment, subjects will review this informational handout prior to taking the screening survey via a URL link. Research staff will inform the participant of the general nature of the study, their privacy rights, expectations for their participation, the voluntary nature of their participation, and that their participation can be withdrawn at any time during the course of the study. Participants will be assured that refusal to participate will not affect their child's medical care in any way. At all times, research staff will make explicit the voluntary nature of their participation. Confidentiality measures will be explained, including assurances that LCH ED staff and law enforcement will not be informed of involvement in the study and/or responses to survey items (see COC). In addition, limits to confidentiality will be explained (e.g., immediate harm to self/others). Before data collection begins, the RAs will also allow time for the participant to review the informational handout, will ask the participant if they have questions, and will ask for the participant to provide a summary of what was explained to them. Participants will be given a copy of the informational handout.

## Consent process:

After obtaining verbal consent, participants will self-administer a computerized screening assessment survey with validated measures assessing for further study eligibility. RAs will stay in the room while the participant takes the survey to be available to assist with patient questions during screening. Study RAs will utilize procedures from prior work to seamlessly integrate the ED-based assessment into the patient's ED stay to avoid interrupting their care.

For remote recruitment, the participant will record their consent to take the survey at the start of the survey after they have read the informational handout and will voluntarily complete the survey via their own personal device. The will take the survey in the privacy of their own home/location.

# Emergency Medicine Prospective Protocol

After completing the screening survey, the RA will determine if the participant is eligible to enroll in the part 2 baseline phase of the study based on a summary of their responses. Participants that are eligible will be notified of the opportunity to take part in an additional phase of the study and the RA will use a written informed consent document to obtain consent for further study participation. This process will occur in either the ED waiting room (a private space) or within the child's ED treatment room. Or remote consenting of part 2 will occur over the phone where the RA will go over the key points of the consent form. The informed consent includes 1) participation in the intervention study with baseline/follow-up assessments and 2) the collection of data using digital photographs. Prior to beginning any data collection with the participant, a trained research assistant will present and explain the comprehensive informed consent document, reviewing the study risks and participants' rights. After all questions are answered to the satisfaction of the participant, and after he/she signs the consent document, then data collection will begin. Participants will be given a copy of the consent form(s). The participant will provide signed consent of the parent permission form via Qualtrics for remote consenting.

For remote recruitment, after the subject completes the screening survey, the RC will determine if the participant is eligible to enroll in the study based on a summary of their responses. Participants that are eligible will be notified via phone, email, or text communication and will have the opportunity to enroll in part 2. The RC will follow the exact same procedures as in person recruitment for part 2 except all procedures will occur over the phone.

## Waiver of the requirement of obtaining a signed consent form:

We are requesting a waiver of the requirement of obtaining a signed consent form for part 1 of this study only. Part 1 of the study includes a brief (~5-10 minute) screening survey that collects one piece of identifying information (5-digit zip code) and presents no more than minimal risk of harm to participants. This screening survey serves the purpose of determining eligibility for part 2 of this study.

## Waiver of informed consent:

We request waiver of informed consent for the retrospective review of visits to the Lurie Children's ED for the purposes of identifying potentially eligible families to screen for eligibility and recruit for participation in the study. The families identified for remote recruitment will be contacted via email, text message and/or phone for initial screening. The remote screening process (Part 1) will include the information sheet distributed via Qualtrics survey or reviewed verbally by the RC over the phone. Any caregiver potentially eligible for Part 2 of the study will complete a phone conversation with a Research Coordinator (RC). Informed consent for participation in part 2 of the study will be conducted verbally over the phone with electronic copies of the consent form delivered to potential participants via email and via a link to a Qualtrics survey. The Qualtrics survey will allow for the collection of electronic signatures from study participants.

A waiver of informed consent will be requested for review of the LCH ED Electronic Medical Record (EMR)/Patient Tracking board, "EPIC," to determine which families to approach for screening. The ability to view LCH EPIC will be for pre-screening purposes only. The Research Assistants will utilize the LCH ED electronic tracking board to continuously monitor incoming patients that meet study inclusion criteria during recruitment shifts. Adult caregivers of children 6 months to 10 years old, who bring their child to the LCH ED for any non-critical illness or injury, will be approached for eligibility screening.

RA tracking logs will contain information regarding patients' age, gender and chief complaint. This information will help to streamline recruitment so that only eligible patients will be

# Emergency Medicine Prospective Protocol

approached and will eliminate approaching non-eligible patients. Minimal clinical data (e.g., sex, race, age, chief complaint) will be collected on ED patients who refuse to participate in the screening survey and on ED patients who the research recruiters fail to approach for the study. Minimal identifiers of potential subjects (first name and birth date) will be kept in order to allow staff time to reconcile recruitment numbers and to avoid re-approaching patients, and this information will be destroyed as soon as possible. The research involves no more than minimal risk and does not adversely affect the rights and welfare of the patients.

This research study requires the use of the child's birth date in order to:

- 1) include the caregivers/parents of children between the ages of 6 months to 10 years in the study
- 2) determine if the child is currently using the child restraint system (CRS) that is optimal for their age according to the 2011 child passenger safety recommendations from the American Academy of Pediatrics (AAP). These recommendations provide the foundation for the educational information that is used in this study to provide caregivers/parents on which CRS to use for their child.

## Safeguard against potential coercion or appearance of coercion:

The risk of potential coercion will be minimized by following standard procedures for obtaining verbal and/or written informed consent from participants. Study personnel will fully explain the study procedures, risks, benefits, and alternatives to participants. The remuneration amount was designed to balance adequate compensation for time without being too large of an amount to be coercive. Participants will also be reminded that study participation is voluntary and that refusing to participate or withdrawing from the study at any time will not result in any negative consequences on their child's care at LCH.

Participants will be allocated ample time to review the verbal informational handout and/or the written informed consent prior to data collection beginning and will be provided time to ask the Research Assistant questions as well. After all questions are answered to the satisfaction of the participant, and after he/she provides verbal consent and/or signs the consent document, then data collection will begin. Participants will be given a copy of the informational handout and/or the written informed consent form.

## **4.6 Vulnerable Populations:**

Caregivers involved in the study may be pregnant. We will not inquire about pregnancy status. The participation of pregnant women involves no more than minimal risk to the mother, with no foreseeable direct risks to the fetus. Children of caregivers enrolled in the study will be subjects to the extent that they will have information collected about their weight and height at ED recruitment and follow-up. In addition, images of the children will be captured in photographs of their child passenger safety behaviors, including seating location and passenger restraint system use. Identifying features of the child (e.g., face) will be obscured in the images before they are saved for analysis. The information captured in photographs is needed to determine if the child is using the size-appropriate CRS and to identify errors in CRS use. Other special vulnerable populations (including fetuses, prisoners, and institutionalized individuals) will not be subjects of the proposed research.

# Emergency Medicine Prospective Protocol

## 5 Study Procedures

### 5.1 Study Intervention or Observational Phase

#### 5.1.1 Visit 1 (baseline visit)

Screening: Caregivers of children who are eligible to approach will complete a self-administered computerized screening survey on a study iPad or remotely via their own personal device to determine eligibility for the full study.

Caregivers who complete the screening survey and meet study eligibility requirements will have the option to enroll in the full study. Eligible caregivers will participate in the informed consent process before determining if they would like to enroll.

Eligible caregivers that enroll in the study will complete the following elements while in the ED or will have the option to finish any of these elements within 5 business days of enrollment remotely via phone.

- A self-administer a computerized baseline survey with validated items collecting information on their child passenger safety practices with their child, barriers/challenges they may experience in using the recommended child restraint, and motivations, etc.
- Tiny Cargo check-in (a car seat check) with the RA to directly observe and record how their child normally rides in a vehicle. We will use the CPaSS tool to collect data during the Tiny Cargo check-in. Caregiver can submit photos during remote recruitment.
- Randomization to the basic TCBD intervention (an ED counseling session plus eHealth after ED discharge) or the control condition (usual ED care with discharge instructions relevant to the child's diagnosis and an information sheet about car safety).
- Caregivers within the TCBD intervention group --Brief motivational interviewing inspired counseling session (~20 minutes).

#### 5.1.2 Visit 2 –Monthly photo requests (over 12 months of study enrollment)

Over the course of the study, all study participants will receive 8 photo requests in months 1, 2, 3, 5, 7, 8, 10, and 11 via text message from the study that asks for them to send us back digital photographs of how their child usually travels in their vehicle. Participants can complete a total of 8 photo requests over the course of the study and will be paid for completing each of them. The CPaSS measure will be used to assess all digital photographs and incorporates elements of seating position, mode selection, CRS fit, and CRS use/misuse drawn from AAP Guidelines and standardized error severity scores for child restraints.

#### 5.1.3 Visit 3 -- (6 month follow-up visit)

A follow-up assessment will be administered at 6- months after the ED visit and will include both a self-administered computerized survey assessment (~15-20 minutes) and a Tiny Cargo check-in (a car seat check) administered by the RA (~10 minutes). The caregiver will have the option to complete the 6-month follow up survey in person at the visit or complete the survey on their own device (phone, iPad, laptop, etc.) prior to the follow-up visit. Allowing participants to complete the follow up assessment prior to the visit, will provide convenience to our participants and shorten the amount of time needed for the in person visit. Additionally, if participants move out of state, country or are unable to get to any of the study follow up site locations, then participants will have the option of completing the Tiny Cargo (TC) check-in (a car seat check) by submitting digital photographs to the study staff via text message or completing the check-in via video chat (e.g., Northwestern zoom, Microsoft teams, skype, duo, google hangout).

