## **3 Investigational Plan**

Study Phase: Remote Recruitment

Study Group: All participants

Setting: Remote

Timing: Recruitment will occur within 6 months of ED visit, potential participants will complete baseline study components within 5 business days of screening eligible for study and agreeing to participate.

For patients that visited the LCH ED, eligibility for screening will be determined from reports generated from Epic. The invitation to complete the eligibility screening questionnaire will be distributed by email, text message, phone call, postcard, flyer in ED room, ED discharge summary paperwork, and MyChart Research Recruitment messages.

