## Monthly photo requests:

- **\*\*See section 9 of IRB app, "supporting documents" for a document called, "Tips & tricks for taking your monthly photo"** --this document will be provided to all participants enrolled in part 2 of the study. The RA will review this document during the ED baseline visit with the participant.
- No matter which group caregivers are assigned into at the baseline visit, we will contact the study participant again starting in 1 month. A member of our study team will send them a photo request via text message. This text message will ask them to share photos of their child as they normally ride in their car.
- These photo requests will be sent to their best phone number. All photos of their child will be sent back to us by the parent/legal guardian.
- They will get requests to submit photos a total of 8 times while taking part in this study (over the next 12 months). We will be asked for these photos during months 1- 5, and Months 7-11 of the study.
- They will get these photo requests only on the days and during the times that they tell us they are able to get messages from us. To update the days and times that they are free to be contacted, caregivers can reach out to our team at by phone or email or text message
- The participant will have a 4 hour window of time to submit their photo requests each month with an additional 4 hour grace period. If a participant submits their photos during their window of time each month and the photos meet the necessary requirements (meaning the RA is able to visibly see all elements of the child sitting in the car seat, then the photos will be approved and the participant will earn \$5 that month. Participants can earn a total of \$40 if they complete all 8 photo requests during their specified window each month and the photos are approved. If the participant completes 4 months of photo submissions in a row, then they will hit a "streak" and will earn an additional \$5. They can hit a "streak" up to 2 times over the course of the study, so they can earn up to an additional \$10.
- Photo message response time (evaluate and response) from study staff will be 24-48 hours. Photo requests will not be sent if the staff are not available to respond during that time window.

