## **5.1.4 End of Study Visit – (12 month follow-up visit)**

The last follow-up assessment will be administered at 12- months after the ED visit and will include both a self-administered computerized survey assessment (~15-20 minutes) and a TC check-in (a car seat check) administered by the RC (~10 minutes). The caregiver will have the option to complete the 12-month follow up survey in person at the visit or complete the survey on their own device (phone, iPad, laptop, etc.) prior to the follow-up visit. Allowing participants to complete the follow up assessment prior to the visit, will provide convenience to our participants and shorten the amount of time needed for the in person visit. Additionally, if participants move out of state, country or are unable to get to any of the study follow up site locations, then participants will have the option of completing the TC check-in (a car seat check) by submitting digital photographs to the study staff via text message or completing the check-in via video chat (e.g., Northwestern zoom, Microsoft teams, skype, duo, google hangout). Caregivers that complete the TC check-in via photo submission or video chat will receive \$5 less in study incentives. The CPaSS tool will be used to collect data during the TC check-ins.

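### Sections 5.1.3 and 5.1.4 date the 6- and 12-month assessments from the ED visit, which conflicts with remote enrolment up to 6 months later and with the enrolment-based study months used elsewhere

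*Combined protocol and SAP*

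**What the plan says.** Section 5.1.3 states: "A follow-up assessment will be administered at 6- months after the ED visit". Section 5.1.4 states: "The last follow-up assessment will be administered at 12- months after the ED visit". These are the only places that tie the two assessments to a date. The follow-up block in Section 3 gives the labels Month 6 and Month 12 and a 1-month window, and Section 3.4.1 says only Month 12.

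Remote recruitment separates the ED visit from enrolment. Section 3 says: "Recruitment will occur within 6 months of ED visit, potential participants will complete baseline study components within 5 business days" of screening eligible and agreeing to take part. Section 4.3 admits a child who is in the ED now or was treated there in the past 6 months, and defines remote outreach as reaching caregivers of children "seen in the Lurie Children's ED in the 6 months prior to the current data". It adds flyer recruitment at affiliate sites, for "families that may not have visited the LCH ED". Under Section 3.2, randomisation follows the baseline survey.

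Elsewhere the clock is enrolment. Section 1.1 places the step-up in intensity at Month 6 of the study. Under Monthly photo requests in Section 3, after assignment at the baseline visit, "we will contact the study participant again starting in 1 month". Section 5.1.2 spreads eight photo requests (Months 1, 2, 3, 5, 7, 8, 10 and 11) over the 12 months of enrolment.

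**The concern.** For a caregiver enrolled in the ED, the ED visit and baseline are at most 5 business days apart and the choice of origin hardly matters. For a remote recruit they can be 6 months apart, and the plan then has two clocks.

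Both affected visits carry weight. The 6-month assessment decides which intervention caregivers are re-randomised to basic or enhanced TCBD (Section 3.2). The 12-month assessment carries the primary outcomes (Section 3.4.1). On the ED clock, a late recruit could be judged a non-responder with little or no intervention received, and the primary endpoint would pool caregivers with different lengths of exposure. The response rates assumed in Section 6.1 come from a 6-month pilot follow-up, so a shorter interval would also weaken their relevance. Two members of staff could schedule the same family differently, each with support in the text.

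**Working it through.** The plan gives no figure for time on study at assessment, so there is none to reproduce. No sample-size or power figure is disputed. The check is a subtraction.

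**Inputs**
- Scheduled times: 6 and 12 months after the ED visit (5.1.3, 5.1.4).
- Delay d from ED visit to enrolment: 0 to 6 months (Sections 3 and 4.3), plus up to 5 business days for baseline (Section 3).
- Start of exposure: randomisation, after the baseline survey (Section 3.2).
- Photo requests before the 6-month visit: Months 1, 2, 3 and 5 (5.1.2).
- Window for each follow-up: 1 month (Section 3).

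**Formula.** Time since randomisation = scheduled time − d, that is 6 − d and 12 − d, ignoring the few days allowed for baseline. The last column lists photo months m with m < 6 − d, counting photo months from enrolment.

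| d (months) | 6-month visit | 12-month visit | Photo requests before the 6-month visit |
|---|---|---|---|
| 0 | 6 | 12 | 1, 2, 3, 5 |
| 1 | 5 | 11 | 1, 2, 3 |
| 2 | 4 | 10 | 1, 2, 3 |
| 3 | 3 | 9 | 1, 2 |
| 4 | 2 | 8 | 1 |
| 5 | 1 | 7 | none |
| 6 | 0 | 6 | none |

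**Baseline allowance.** Five business days are about 7 calendar days, or 7 / 30.4375 = 0.23 month. At d = 6 the visits then fall at 0 − 0.23 = −0.23 and 6 − 0.23 = 5.77 months, so the first assessment is due before baseline is complete.

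**Window.** If the 1-month window runs after the due date (an assumption; the text does not say) and is used in full, the times become 7 − d and 13 − d. At d = 6 that is 1 and 7 months.

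**Month 7/8 call.** If this call to the enhanced group is counted from enrolment, it should precede the 12-month visit. But 12 − d is 8 or less once d ≥ 4, and 7 or less once d ≥ 5. From d = 5 the call could come at or after the primary assessment. At d = 6, the Month 7, 8, 10 and 11 photo requests would all follow that assessment.

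**After the fix.** Counted from randomisation, the visits fall at 6 and 12 months for everyone, or up to 7 and 13 with the window, whatever the value of d.

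**The case against.** The strongest reply is that the ED wording is a leftover from in-person recruitment and means baseline. There is good support for this. Table 1 in Section 3.3 labels the first time point as ED and baseline together. The payment table in Section 10.3 lists the baseline visit under an emergency room heading. Section 3 sends remote recruits through the same study flow, and the consent process in Section 4.5 gives them the same part 2 procedures by phone. The month numbering in Sections 1.1, 3 and 5.1.2 fits an enrolment clock. The literal reading also cannot be operated for late recruits, which suggests that nobody intended it.

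This stands as evidence of intent, and it rules out inferring that remote recruits will in fact be assessed at 0 and 6 months. It does not remove the contradiction: the two sections that schedule the visits still name the other origin, and no passage sets a different one for remote recruits.

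Three further inferences are tempting and not supported.
- **Mean exposure of 3 and 9 months.** This follows from a mean delay of 3 months, as with delays uniform over 0 to 6, and would cover remote recruits only. The documents give neither the delays nor the remote share. Flyers in ED rooms and discharge paperwork recruit at or near the visit; postcards are sent only after other contact has failed.
- **No start date for any affiliate-site family.** Some affiliate sites are EDs, and 5.1.3 does not restrict the visit to the LCH ED. The gap is clear only for Immediate Care Centers.
- **Bias toward one arm.** Delay is fixed before randomisation, so it is balanced between arms in expectation.

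**Conclusion.** The plan contradicts itself on the time origin of its two main assessments. Read literally, 5.1.3 and 5.1.4 put remote recruits at 0 to 6 months after randomisation when re-randomisation is decided, and at 6 to 12 months at the primary endpoint. The extremes of 0 and 6 months need the full 6-month delay and no use of the window. For families from Immediate Care Centers the rule may have no date to start from.

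The documents do not show that visits will be run this way, and average exposure cannot be computed from them. If the ED clock were followed, the expected effect would be variable and shorter exposure, dilution of the treatment effect, and misclassified Month-6 non-response. Remote recruits may not be a small group, since Section 4.3 notes that study tasks have gone fully remote. The range rests only on the documents' own figures and is certain as arithmetic; how far it would be realised is unknown.

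**What to change.** In Sections 5.1.3 and 5.1.4, replace the ED visit with randomisation as the point from which 6 and 12 months are counted, and keep the existing 1-month window. State once that all study months, including the photo requests, the text messages and the Month 7/8 call, count from that same date. This also gives a start date to families with no ED visit.

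The cost is two edited sentences and one statement of the common origin, with no extra visits or data. If staff already schedule from baseline, the amendment essentially brings the text into line with practice.
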